### Conduct of Part 2 (DG 2, 40 mg BI 474121) – if applicable:

6 subjects will receive non-randomized treatment, all subjects on active.

After DG 2 (40 mg) a documented data review based on an analysis of preliminary data (see Section 7.4) will take place to decide whether to continue with Part 3 or to terminate the trial (see Figure 1.4: 1 and Section 3.3.4.3).

If the desired PD effect is observed after administration of 40 mg BI 474121, the trial continues with Part 3 given the observed safety profile allows to proceed.

If the desired PD effect is not observed after administration of 40 mg BI 474121, the sponsor reserves the right to terminate the trial.

#### **Minimum data set to be reviewed after Part 2 (DG 2, 40 mg BI 474121)**

Data from at least 4 subjects on active (from DG 2) and at least 3 subjects on placebo (from DG 1) needs to be evaluated to assess the PD effect.

For safety data, no minimum data set is specified, since in Part 3 of the trial lower doses are administered. However, the documented data review includes the review of all available safety data.

The decision about the further conduct of the trial based on the preliminary data analysis will be made jointly by the Principal Investigator (PI), the Team Member Medicine (TMM), and the Clinical Trial Leader (CTL) or their respective authorised deputy. The documented data reviews may be conducted by video/telephone conference. The CTL is responsible for the organisation and minutes of the reviews. Minutes will be signed off by the PI (or an authorised deputy), the CTL (or authorised deputy), and the TMM and will be filed in the ISF and TMF.

**Conduct of Part 3 (DG 3, 10 mg BI 474121 and DG 4, 2.5 mg BI 474121) – if applicable:** 8 subjects will receive randomized treatment, all subjects on active, 4 subjects in DG 3 (10 mg) and 4 subjects in DG 4 (2.5 mg).

### **3.2 DISCUSSION OF TRIAL DESIGN, INCLUDING THE CHOICE OF CONTROL GROUP**

The design described in Section 3.1. was chosen to support with two pre-defined preliminary data analyses early decision(s) about further trial conduct (see Figure 1.4:1). This approach seeks to avoid that subjects are unnecessarily exposed to drug- and procedure-related risks.

With the same consideration (i.e. reducing the number of subjects exposed to drug- und procedure-related risks), placebo subjects were only included in Part 1 of the trial.

Since no sequence effects are expected, it appears acceptable to use the placebo subjects from Part 1 for the PD assessment in Part 2.

The open-label treatment in Parts 2 and 3 of the trial is not expected to bias results, since the primary and secondary study endpoints are derived from measurement of plasma and CSF concentrations of the analytes and placebo subjects from part 1 serve as control.

### 3.3 SELECTION OF TRIAL POPULATION

It is planned that at maximum 24 healthy male subjects will enter the study. They will be recruited from the volunteers' pool of the trial site.

Only male subjects will be included in the study because no data on reproductive toxicology are available at this time.

A log of all subjects enrolled into the trial (i.e. who have signed informed consent) will be maintained in the ISF irrespective of whether they have been treated with investigational drug or not.

#### 3.3.1 Main diagnosis for trial entry

The study will be performed in healthy male subjects.

#### 3.3.2 Inclusion criteria

Subjects will only be included in the trial if they meet the following criteria:

1. Healthy male subjects according to the assessment of the investigator, as based on a complete medical history including a physical examination, vital signs (BP, PR), 12-lead ECG, and clinical laboratory tests
2. Age of 18 to 65 years (inclusive)
3. BMI of 18.5 to 29.9 kg/m^2 (inclusive)
4. Signed and dated written informed consent prior to admission to the study, in accordance with GCP and local legislation

#### 3.3.3 Exclusion criteria

Subjects will not be allowed to participate if any of the following general criteria apply:

1. Any finding in the medical examination (including BP, PR or ECG) deviating from normal and assessed as clinically relevant by the investigator
2. Repeated measurement of systolic blood pressure outside the range of 90 to 150 mmHg, diastolic blood pressure outside the range of 50 to 90 mmHg, or pulse rate outside the range of 45 to 90 bpm
3. Any laboratory value outside the reference range that the investigator considers to be of clinical relevance
4. Any evidence of a concomitant disease assessed as clinically relevant by the investigator
5. Gastrointestinal, hepatic, renal, respiratory, cardiovascular, metabolic, immunological or hormonal disorders assessed as clinically relevant by the investigator

6. Cholecystectomy or other surgery of the gastrointestinal tract that could interfere with the pharmacokinetics of the trial medication (except appendectomy or simple hernia repair)
7. Diseases of the central nervous system (including but not limited to any kind of seizures or stroke), and other relevant neurological or psychiatric disorders
8. History of relevant orthostatic hypotension, fainting spells, or blackouts
9. Chronic or relevant acute infections
10. History of relevant allergy or hypersensitivity (including allergy to the trial medication or its excipients)
11. Use of drugs within 30 days of planned administration of trial medication that might reasonably influence the results of the trial (including drugs that cause QT/QTc interval prolongation)
12. Intake of an investigational drug in another clinical trial within 30 days of planned administration of investigational drug in the current trial, or concurrent participation in another clinical trial in which investigational drug is administered
13. Smoker (more than 10 cigarettes or 3 cigars or 3 pipes per day)
14. Inability to refrain from smoking on specified trial days
15. Alcohol abuse (consumption of more than 30 g or 3 alcoholic units per day)
16. Drug abuse or positive drug screening
17. Blood donation of more than 100 mL within 30 days of planned administration of trial medication or intended blood donation during the trial
18. Intention to perform excessive physical activities within one week prior to the administration of trial medication or during the trial
19. Inability to comply with the dietary regimen of the trial site
20. A marked baseline prolongation of QT/QTc interval (such as QTc intervals that are repeatedly greater than 450 ms in males) or any other relevant ECG finding at screening
21. A history of additional risk factors for Torsade de Pointes (such as heart failure, clinically relevant hypokalaemia, or family history of Long QT Syndrome)
22. Subject is assessed as unsuitable for inclusion by the investigator, for instance, because the subject is not considered able to understand and comply with study requirements, or has a condition that would not allow safe participation in the study
23. Male subjects with WOCBP partner who are unwilling to use a highly effective method of birth control from time point of administration of trial medication until 90 days thereafter. Highly effective methods of birth control are:
  - Male subject is sexually abstinent
  - Male subjects is vasectomised (vasectomy at least 1 year prior to enrolment), *plus* condom in male subject
  - Use of intrauterine device (IUD) or intrauterine hormone-releasing system (IUS)
  - Use of progestogen-only hormonal contraception by female partner that inhibits ovulation (only injectables or implants), *plus* condom in male subject
  - Use of combined (estrogen and progestogen containing) hormonal contraception by female partner that prevents ovulation (oral, intravaginal or transdermal), *plus* condom in male subject

- Female partner is surgically sterilised (including hysterectomy)
- Female partner is postmenopausal, defined as no menses for 1 year without an alternative medical cause (in questionable cases a blood sample with FSH above 40 U/L and estradiol below 30 ng/L is confirmatory)

Sperm donation is not allowed from the time point of drug administration until 90 days thereafter.

In addition, the following trial-specific exclusion criteria apply:

24. ALT (alanine transaminase), AST (aspartate transaminase), exceed 1.5 x upper limit of normal range at screening, confirmed by a repeat test
25. Estimated glomerular filtration rate (eGFR) according to CKD-EPI formula below or equal 60 ml/min at screening, confirmed by a repeat test
26. History of migraine or other types of headache more than twice/month, history of intervertebral disc disease or chronic significant low back pain
27. Use of blood thinning compounds within 10 days (for low and high molecular weight heparins, aspirin) and within 30 days (for all other drugs with anticoagulatory effects) of spinal catheter placement
28. History or presence of head injuries with documented loss of consciousness for >5 minutes
29. History of spinal cord compression
30. An infection or inflammation of the skin in or in close proximity to the area of the lumbar puncture site or has absolute or relative anatomic abnormalities that would be a contraindication to lumbar puncture
31. Spinal surgery and spinal deformities incompatible with lumbar puncture and/or spinal catheter insertion. Microdiscectomy procedures are allowed.
32. Signs of increased intracranial pressure as determined by fundoscopy

In addition, the following SARS-CoV-2 specific exclusion criterion applies

33. A positive PCR test for SARS-CoV-2 and clinical symptoms suggestive for this disease at Day -1

For study restrictions, refer to Section [4.2.2](#).

### **3.3.4 Withdrawal of subjects from treatment or assessments**

Subjects may discontinue trial treatment or withdraw consent to trial participation as a whole ('withdrawal of consent') with very different implications; please see Sections [3.3.4.1](#) and [3.3.4.2](#) below.

If a subject is removed from or withdraws from the trial prior to the administration of trial medication, the data of this subject will not be entered in the case report form (CRF) and will not be reported in the clinical trial report (CTR). If a subject is removed from or withdraws from the trial after the administration of trial medication, this will be documented and the reason for discontinuation must be recorded in the CRF; in addition, the data will be included

in the CRF and will be reported in the CTR. At the time of discontinuation, a complete end of trial examination will be performed, if possible, and the information will be recorded in the CRF. If the discontinuation occurs before the end of the REP (see Section [1.2.2](#)), the discontinued subject should if possible be questioned for AEs and concomitant therapies at or after the end of the REP in order to ensure collection of AEs and concomitant therapies throughout the REP, if not contrary to any consent withdrawal of the subject.

Since the risks of drug exposure of a (pregnant) female partner of a male study participant via the seminal fluid are yet unknown, adequate contraception as outlined in Section [3.3.3](#) is a prerequisite for participation in the study.

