				-20:00	13:00	Lunch											
				-16:00	17:00	Snack											
			-14:00	19:00	Dinner												
Treatment period	2	1	-2:00	07:00	Allocation to treatment  Placement of spinal catheter 		X 	X 					X 	X 			
			-1:00	08:00				X 									
			-0:10	08:50				X 									
			0:00	09:00	Drug administration 												
			0:15	09:15				X									
			0:30	09:30				X	X								
			1:00	10:00				X	X					X			
			1:30	10:30				X	X								
			2:00	11:00	240 mL fluid intake			X	X					X			
			3:00	12:00				X	X								
			4:00	13:00	240 mL fluid intake, there- after lunch 			X	X					X	X		
			5:00	14:00				X	X								
			6:00	15:00				X	X								
			7:00	16:00				X	X								
			8:00	17:00	Snack (voluntary) 			X	X					X	X		
			10:00	19:00				X	X								
			11:00	20:00	Dinner												
			12:00	21:00				X	X								
			14:00	23:00				X	X						X		
				2	24:00	09:00	Removal of spinal catheter, Breakfast 	X B,12	X	X				X 	X	X	
					28:00	13:00	Lunch 									X	
					32:00	17:00	Snack (voluntary) 										
					34:00	19:00	Dinner 			X							
					36:00	21:00										X	X
	3	48:00	09:00	Confirmation of fitness, discharge from trial site, breakfast (voluntary) 		X			▼	X	X 	X	X				
	4	72:00	09:00	Ambulatory visit	X B	X					X 	X	X				
FU	3	8 to 14			End of trial (EoTrial) 	X C				X	X	X	X				

1. Subject must be informed and written informed consent obtained prior to starting any screening procedures. Screening procedures include physical examination, check of vital signs, ECG, safety laboratory (including drug screening), demographics (including determination of body height and weight, smoking status and alcohol history), relevant medical history, concomitant therapy and review of inclusion/exclusion criteria.
2. The time is approximate; the procedure is to be performed and completed within the 3 h prior to drug administration.
3. If several actions are indicated at the same time, the intake of meals will be the last action.
4. At the end of trial visit the EoTrial medical examination includes physical examination, vital signs, ECG, safety laboratory, recording of AEs and concomitant therapies, and visual inspection of lumbar puncture site.

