#### Procedure-related risks

Subjects participating in the trial will undergo a serial CSF sampling via an indwelling spinal catheter. The most common adverse events associated with the serial CSF sample collection are headache, nausea, light headedness, retro-ocular pressure sensation, dizziness, muscle pain of the lower back, neck pain, back pain, catheter site pain, back discomfort and tenderness of the spinal catheter insertion site [R20-0666].

However, the procedure is potentially associated with rare but more severe adverse events, such as epidural infection, meningitis, spinal cord or nerve root trauma, spinal/epidural hematoma and cerebral herniation [R20-2943].

In this publication [R20-0666], the procedural-related risks are summarized with focus on procedural (i.e. post-spinal) headache:

[figure not shown]
In 71 subjects (25 females, 56 males), mean age 45 years, 24 (33.8%) subjects experienced post-spinal headache. The mean duration of headache was 120 hours. Thirteen (18.3%) subjects required an epidural blood patch. Sciatic pain, paraesthesia and muscle cramping were noted as adverse events in subjects where a spinal catheter was placed. Specifically, after 24 h serial CSF sampling regime procedural headache is reported as 16 out of 43 subjects (37.2%).

The total volume of sampled CSF during this entire trial will be not more than 50 mL. It is expected that in a healthy subject the collected CSF volume will be completely substituted via arachnoidal production as the rate of CSF production is about 500 mL/day.

The use of an indwelling venous catheter or venepuncture for e.g. blood sampling may result in mild bruising, and in rare cases, in transient inflammation of the wall of the vein, or nerve injury, potentially resulting in paraesthesia, reduced sensibility, and/or pain for an indefinite period.

The total volume of blood withdrawn per subject during the entire study will not exceed the volume of a normal blood donation (500 mL). No health-related risk to healthy subjects is expected from withdrawal of this volume of blood.

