## 5.2.5.2 Adverse event collection and reporting

### 5.2.5.2.1 AE collection

Upon enrolment into a trial, the subject's baseline condition is assessed (for instance, by documentation of medical history/concomitant diagnoses), and relevant changes from baseline are noted subsequently.

Subjects will be required to report spontaneously any AEs as well as the time of onset, end time, and intensity of these events. In addition, each subject will be regularly assessed by the medical staff throughout the clinical trial and whenever the investigator deems necessary. As a minimum, subjects will be questioned for AEs (and concomitant therapies) at the time points indicated in the [Flow Chart](#). Assessment will be made using non-specific questions such as 'How do you feel?'. Specific questions will be asked wherever necessary in order to more precisely describe an AE.

A carefully written record of all AEs shall be kept by the investigator in charge of the trial. Records of AEs shall include data on the time of onset, end time, intensity of the event, and any treatment or action required for the event and its outcome.

The following must be collected and documented on the appropriate CRF(s) by the investigator:

- From signing the informed consent onwards until an individual subject's end of trial:
  - All AEs (serious and non-serious) and all AESIs
  - The only exception to this rule are AEs (serious and non-serious) and AESIs in Phase I trials in healthy volunteers, when subjects discontinue from the trial due to screening failures prior to administration of any trial medication. In these cases, the subjects' data must be collected at trial site but will not be entered in the CRF or trial database and will not be reported in the CTR.
- After the individual subject's end of trial:
  - The investigator does not need to actively monitor the subject for AEs but should only report any occurrence of cancer and related SAEs and related AESIs of which the investigator may become aware of by any means of communication, e.g. phone call. Those AEs should, however, not be reported in the CRF.

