## Spinal catheter for CSF sampling

On day 1, prior to drug administration, the spinal catheter is inserted. The spinal catheterisation procedure, as well as CSF sampling and removal of catheter follows medical standards with appropriate safety measures as laid down in the [REDACTED] SOP on continuous CSF sampling using a spinal catheter [[c34094265](#)].

For syringes used and volumes drawn see Section [5.4.1](#) of the CTP. In this respect, the [REDACTED] SOP does not apply.

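### Protocol Sections 3.3.4 and 5.2.5.2.1 contradict each other on recording adverse events in a subject who is catheterised but withdrawn before dosing

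*Protocol*

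**What the plan says.** Protocol Section 3.3.4 sets its cut-off at dosing. It applies if a subject is removed, or if he "withdraws from the trial prior to the administration of trial medication, the data of this subject will not be entered in the case report form". The same sentence excludes those data from the CTR, and it makes no exception for AEs or for procedures already carried out.

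Section 5.2.5.2.1 sets a different cut-off. AEs, serious or not, go on the CRF "From signing the informed consent onwards until an individual" subject's trial ends. The sole exception is "when subjects discontinue from the trial due to screening failures prior to administration of any trial medication". Even then the site must collect the data.

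On timing, Section 6.2.2 states: "On day 1, prior to drug administration, the spinal catheter is inserted". The Flow Chart puts allocation and catheter placement in the same row at about -2:00, in Visit 2 under the treatment period. Its footnote 2 adds that "the procedure is to be performed and completed within the 3 h prior to drug administration". Footnote 9 describes three baseline CSF samples, all taken before dosing.

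On risk, Section 1.4 says that "the procedure is potentially associated with rare but more severe adverse events" and names "epidural infection, meningitis, spinal cord or nerve root trauma, spinal/epidural hematoma and cerebral herniation".

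On analysis, Protocol Section 7.3.1 and SAP Section 6.3 both require a dose for membership of the treated set (TS). SAP Section 7.8 runs all safety analyses on the TS, and SAP Table 6.3: 1 puts disposition on it as well.

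**The concern.** The invasive procedure starts before the point from which Section 3.3.4 keeps data. Take a man who is allocated and catheterised, has a complication during or soon after insertion, and leaves the trial undosed. One section tells the site to keep him out of the CRF and CTR. The other tells the site to enter his AEs.

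If the site follows 3.3.4, the loss is selective, because an insertion complication is missing exactly when it was bad enough to stop dosing. Section 3.3.5 allows non-completers to be replaced, so the CTR could also show fewer catheterisations than were done. Sections 1.4 and 3.2 justify the staged design partly by limiting exposure to procedural risk. A complete account of that exposure should not depend on which section the site happened to read.

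**Working it through.** No stated figure is at issue, so the check is mainly a comparison of text.

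**Step 1: is such a man a screening failure?** The documents point mostly to no. The Flow Chart gives screening as Visit 1, Days -21 to -2, and puts catheter placement in Visit 2. Section 8.3.1 requires documented eligibility before allocation, and allocation shares a Flow Chart row with the catheter. Against this, Protocol Section 7.3.5 and SAP Table 6.1: 2 label everything before drug intake as screening, but that is an analysis phase for sorting events. The fair statement is that he is not evidently a screening failure.

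**Step 2: where does his catheter complication appear?**

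| Record | If 3.3.4 is followed | If 5.2.5.2.1 is followed |
|---|---|---|
| Site records | Yes | Yes |
| SAE form to sponsor within 24 h, if serious (5.2.5.2.2) | Yes | Yes |
| CRF | No | Yes |
| CTR | No | Not barred, but no planned display names him |
| TS safety tables and TS disposition | No | No |

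The CRF and CTR rows hold the contradiction. The last row is a gap under both readings.

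**Step 3: how many men could this concern?** The documents give no rate of pre-dose complications that prevent dosing. The headache figures in Section 1.4 (24/71 = 33.8%; 16/43 = 37.2%) cover the whole procedure and cannot stand in for it. With an assumed per-subject probability p and 24 catheterised men (the planned total), the expected number is 24p and the chance of at least one is 1 - (1 - p)^24:

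| Assumed p | Expected number | Chance of at least one |
|---|---|---|
| 1% | 24 × 0.01 = 0.24 | 1 - 0.99^24 = 21% |
| 2% | 24 × 0.02 = 0.48 | 1 - 0.98^24 = 38% |
| 5% | 24 × 0.05 = 1.2 | 1 - 0.95^24 = 71% |
| 10% | 24 × 0.10 = 2.4 | 1 - 0.90^24 = 92% |

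These values of p are assumptions. At 1% the chance of no such man is 79%, and the true p could be lower.

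**The case against.** A reader might infer that such a complication vanishes from the trial's safety record altogether. The documents do not support that. Section 5.2.5.2.1 itself calls for CRF entry and, for excepted subjects, site records. Section 5.2.5.2.2 sends SAEs, and non-serious AEs relevant to them, to the sponsor within 24 h with no condition that the subject was dosed. Section 5.2.5.2.3 requires follow-up of all AEs. Section 3.3 keeps a log of everyone who consented, treated or not. Events before dosing in men who are later dosed are unaffected.

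A reader might also infer a measurable bias in a reported procedural risk. That does not stand either. The stated safety objective concerns BI 474121, no endpoint estimates procedural risk, and the Section 1.4 list gives no onset times. The catheter also stays in until 24 h after dosing, so the pre-dose window is a small part of the time at risk.

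Two further arguments have some force:

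- **Section 3.3.4.1, item 4** covers a subject who cannot receive treatment for medical reasons and says that he remains in the trial. On that reading 3.3.4 would not apply to him. With a single dose not yet given, the fit is debatable, and it adds one more reading for the site to choose from.
- **Listings.** Protocol Section 7.3.1 and SAP Section 7 promise listings of individual data, and SAP Section 6.1 includes the screening phase in Appendix 16.2. These could hold him, but only if he is in the CRF, which is the point in dispute.

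**Conclusion.** The contradiction is real and can be read directly from the text. For a man catheterised but undosed, Section 3.3.4 forbids the CRF entry that Section 5.2.5.2.1 requires. If 3.3.4 is followed, a complication that prevents dosing is absent from the CRF and CTR. An SAE still reaches the sponsor, and an isolated non-serious event stays at the site. Whichever section is followed, the event is outside the TS safety tables.

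The conclusion rests on one interpretive step, that a man allocated and catheterised on Day 1 is not a screening failure. The number affected may be zero. No primary or secondary endpoint and no drug-safety table changes. It is a flaw in safety recording and reporting that should be corrected because the wording is contradictory and the correction is small.

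**What to change.** - **Protocol 3.3.4:** align with 5.2.5.2.1 by limiting the no-CRF, no-CTR rule to screening failures who leave before catheter placement is started. From the start of placement, enter AEs, SAEs and the reason for withdrawal in the CRF and report them in the CTR. Reconcile the wording with 3.3.4.1, item 4.
- **SAP:** beside the TS, add a listing of subjects catheterised but not dosed, with their AEs, and state the number catheterised. The TS and all planned tables stay as they are.

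The cost is one sentence in the protocol, one line in the SAP, and CRF entry for however few subjects are concerned. The small downside is a short listing for men who never received trial medication. No dose, schedule or clinical rule changes.
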